3.0 PATIENT SELECTION

3.1 Inclusion Criteria

1. Histologically confirmed diagnosis of nonresectable or metastatic soft tissue sarcoma. The following histologies are excluded: embryonal rhabdomyosarcoma, chondrosarcoma, osteosarcoma, Ewing tumors, primitive neuroectodermal tumors, gastrointestinal stromal tumors, dermatofibrosarcoma protuberans, inflammatory myofibroblastic sarcoma, and mixed mesodermal tumors of the uterus.

2. Evaluable disease by imaging or physical exam OR measurable disease defined as at least one lesion that can be accurately measured in at least one dimension (longest diameter to be recorded) as ≥ 10 mm with CT scan, as ≥ 20 mm by chest x-ray, or ≥ 10 mm with calipers by clinical exam.
3. Not a candidate for chemotherapy as determined by the treating physician.
4. Age ≥ 18 years
5. ECOG performance status ≤ 2 (see Appendix A).
6. Normal bone marrow and organ function as defined below:
 - a. Absolute neutrophil count $\geq 1,500/\text{mcl}$
 - b. Platelets $\geq 100,000/\text{mcl}$
 - c. Hemoglobin ≥ 9.0 g/dL
 - d. PT or INR $\leq 1.2 \times$ IULN (if not receiving anticoagulation therapy)
 - e. PTT $\leq 1.2 \times$ IULN (if not receiving anticoagulation therapy)
 - f. Total bilirubin $\leq 1.5 \times$ IULN or $\leq 3.0 \times$ IULN with normal AST and ALT in patients with Gilbert's disease
 - g. AST(SGOT)/ALT(SGPT) $\leq 2.5 \times$ IULN
 - h. Creatinine ≤ 1.5 mg/dL OR creatinine clearance ≥ 30 mL/min/1.73 m² for patients with creatinine levels above 1.5 mg/dL
 - i. UPC < 1 (in like units) or, if UPC ≥ 1 , 24-hour urine protein < 1 g; use of urine dipstick for renal function assessment is not acceptable.

Notes:

Subjects may not have had a transfusion within 7 days of screening assessments. Concomitant elevation of bilirubin and AST/ALT above the IULN is not allowed.

Patients receiving anticoagulation therapy are eligible if their INR is stable and within the recommended range for the desired level of anticoagulation.

7. Ability to swallow and retain oral tablets.
8. Women of childbearing potential must agree to use adequate contraception (hormonal or barrier method of birth control, abstinence) prior to study entry and for the duration of study participation. Should a woman become pregnant or suspect she is pregnant while participating in this study, she must inform her treating physician immediately.
9. Ability to understand and willingness to sign an IRB approved written informed consent document.

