6.0 DOSE DELAYS/DOSE MODIFICATIONS

As a general rule, if dose reduction of pazopanib is necessary, the dose should be reduced stepwise by 200 mg at each step, and the patient should be monitored for approximately 10 to 14 days at each dose level. If toxicity does not abate during this monitoring time, the pazopanib may need to be interrupted and/or the dose further decreased with continued monitoring for an additional 10-14 days at each dose level, and so on.

If the toxicity has abated with reduction of the dose and dose re-escalation is considered safe by the investigator, the pazopanib dose can then be increased step-wise back to the pre-event dose (in 200 mg increments, after monitoring for 10-14 days at each dose level to ensure that toxicity did not recur or worsen).

Dose Modification Algorithms for Potential Treatment-Related Adverse Events

AE Terms & Descriptions	Dose Modification Algorithms
Hypertension	
(A). Asymptomatic and persistent SBP of ≥ 140 - < 170 mmHg, or DBP ≥ 90 - < 110 mmHg, or a clinically significant increase in DBP of 20 mmHg (but still below 110 mmHg).	Step 1. Continue pazopanib at the current dose. Step 2. Adjust current or initiate new antihypertensive medication(s). Step 3. Titrate antihypertensive medication(s) during next 2 weeks as indicated to achieve well-controlled ^a blood pressure (BP). If BP is not well-controlled within 2 weeks, consider referral to a specialist and go to scenario (B).
(B). Asymptomatic SBP ≥ 170 mmHg, or DBP ≥ 110 mmHg, or failure to achieve well-controlled BP within 2 weeks in scenario (A). (A).	Step 1. Consider reducing or interrupting pazopanib, as clinically indicated. Step 2. Adjust current or initiate new antihypertensive medication. Step 3. Titrate antihypertensive medication(s) during next 2 weeks as indicated to achieve well-controlled BP. Step 4. Once BP is well-controlled, restart pazopanib dose-reduced by 200 mg if it was interrupted.
(C). Symptomatic hypertension or recurring SBP ≥ 170 mmHg, or DBP ≥ 110 mmHg, despite modification of antihypertensive medication(s)	Step 1. Interrupt pazopanib. Step 2. Adjust current or initiate new antihypertensive medication(s). Step 3. Titrate antihypertensive medication(s) during next 2 weeks as indicated to achieve well-controlled BP. Referral to a specialist for further evaluation and follow-up is also recommended. Step 4. Once BP is well-controlled, restart pazopanib dose-reduced by 200 mg.

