(D). Refractory hypertension unresponsive to above interventions.	Discontinue pazopanib and continue follow-up per protocol.
Proteinuria	
UPC < 3	Continue pazopanib at the current dose; monitor as clinically indicated
UPC ≥ 3 or 24-h urine protein ≥ 3 g	Step 1. Interrupt pazopanib. Step 2. Weekly UPC or 24-hr urine protein monitoring until

AE Terms & Descriptions	Dose Modification Algorithms
	
UPC is <3 or 24-hr urine protein is <3 g. Then restart pazopanib dose-reduced by 200 mg.
 
Step 3. If UPC ≥ 3 or 24-h urine protein ≥ 3g recurs, repeat steps 1 and 2
 
Step 4. If UPC ≥ 3 or 24-hr urine protein ≥ 3 recurs and the pazopanib dose can no longer be reduced, discontinue pazopanib and continue follow-up per protocol.

Hemorrhage/Bleeding: Investigate and document underlying etiology of the bleeding	
Grade 1	
For hemoptysis, interrupt pazopanib and consider whether further treatment with pazopanib is appropriate.
 
For other grade 1 hemorrhage/bleeding event, continue pazopanib at the current dose; monitor as clinically indicated.

Grade 2	
Step 1. If pulmonary or GI bleed (other than hemorrhoidal bleeding), discontinue pazopanib and continue follow-up per protocol. Otherwise, interrupt pazopanib until the AE resolved to \leq grade 1.
 
Step 2. Restart pazopanib; consider reducing dose and monitor as clinically indicated.

Grade 3 or 4, or recurrent \geq grade 2 event after dose interruption/reduction.	Discontinue pazopanib and continue with follow-up per protocol.
Venous Thrombosis (DVT, PE)	
Grade 2	Continue pazopanib at the current dose; monitor as clinically indicated

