Other Clinically Significant Drug-Related Adverse Events^b	
Grade 1	Continue pazopanib; monitor as clinically indicated.
Grade 2 or 3, if clinically significant	Step 1. Interrupt pazopanib until toxicity resolves to \leq Grade 1. Step 2. Restart pazopanib dose-reduced by 200 mg and monitor as clinically indicated.
Grade 4	Discontinue pazopanib and continue follow-up per protocol. (study drug can be interrupted for up to 28 days)
Prolongation of QTc Interval: If the QTc is prolonged, the ECG should be manually read to ensure accuracy of the reading. The values below refer to manually-read ECGs.	
QTc \geq 480-500 msec	Continue pazopanib; monitor as clinically indicated.
QTc \geq 500 msec	Discontinue pazopanib and continue follow-up per protocol.

a. Well-controlled BP defined as SBP <140 mmHg and mean DBP <90 mmHg.

b. AEs are graded according to NCI Common Terminology Criteria for Adverse Events v4.0 (NCI CTCAE v4)

Guidelines for Management of Treatment Emergent Hepatotoxicity

Event	Dose Modification Algorithms
(A). ALT of $\leq 3.0 \times \text{ULN}$	Continue pazopanib at current dose with full panel LFTs ^a monitored as per protocol.
(B). ALT $>3.0 \times \text{ULN}$ to $\leq 8.0 \times \text{ULN}$ without bilirubin elevation (defined as total bilirubin ^b $<2.0 \times \text{ULN}$ or direct bilirubin $\leq 35\%$) and without hypersensitivity symptoms (e.g., fever, rash)	Step 1. Continue pazopanib at current dose levels. Step 2. Monitor subject closely for clinical signs and symptoms; perform full panel LFTs ^a weekly or more frequently if clinically indicated until ALT is reduced to grade 1.

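### Section 6.0 proteinuria rows: when UPC and 24-hour protein fall on opposite sides of 3, one pair of results can call for two actions, and restart can be met while the interruption condition still holds

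*Combined protocol and SAP*

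**What the plan says.** The proteinuria part of the dose-modification table in Section 6.0 has two rows.

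- The first is headed by UPC below 3 and does not mention the 24-hour collection. Its instruction is "Continue pazopanib at the current dose; monitor as clinically indicated".
- The second is headed "UPC ≥ 3 or 24-h urine protein ≥ 3 g". Step 1 interrupts pazopanib. Step 2 begins "Weekly UPC or 24-hr urine protein monitoring until" and is completed by the restart condition "UPC is <3 or 24-hr urine protein is <3 g. Then restart pazopanib dose-reduced by 200 mg". Step 3 repeats Steps 1 and 2 if the finding recurs. Step 4 discontinues pazopanib if it recurs and the dose can no longer be lowered.

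The study calendar in Section 10.0 lists UPC at screening, on Day 1 of each cycle through cycle 6, on Day 1 of even-numbered cycles after that, and at end of treatment. It lists no 24-hour urine collection.

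**The concern.** A dose-modification table should send each set of results to one action, and a restart condition should not be true while the condition that stopped the drug is also true. The proteinuria rows fail both tests when the two measures disagree. The first row looks at UPC only, while the second reacts to either measure. The restart condition also accepts either measure, and no sentence says that it must be the one that triggered the interruption.

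Sites could therefore follow the text faithfully and act differently on identical results: one leaves the dose unchanged, another interrupts, and a third restarts 200 mg lower while one measure is still at or above the protocol's own limit. At stake are uniform exposure to pazopanib and uniform safety handling across sites.

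**Working it through.** The plan states no figure on this point, so the check is one of logic. Let U be the UPC and P the 24-hour urine protein in grams. The inputs are the two proteinuria rows of Section 6.0:

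- Unchanged dose (first row): C = (U < 3)
- Interrupt (second row, heading): I = (U ≥ 3 or P ≥ 3)
- Restart 200 mg lower (second row, Step 2): R = (U < 3 or P < 3)

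The four possible combinations, with illustrative values on each side of the limit, are:

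| U | P (g) | C: dose unchanged | I: interrupt | R: restart condition | Result |
|---|---|---|---|---|---|
| 3.5 | 3.5 | no | yes | no | consistent |
| 3.5 | 2.5 | no | yes | yes | I and R both true |
| 2.5 | 3.5 | yes | yes | yes | C and I both true; I and R both true |
| 2.5 | 2.5 | yes | no | yes | consistent |

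**Two rows at once.** C and I hold together exactly when U < 3 and P ≥ 3. This conflict does not depend on how the restart step is read.

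**Entry and exit at once.** R fails only when both measures are at or above 3, so it is the negation of (U ≥ 3 and P ≥ 3). It is not the negation of I, which is (U < 3 and P < 3). I and R therefore hold together whenever exactly one measure is at or above 3, which covers both discordant combinations.

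**The two values need not come from the same day.** Step 2 lets weekly follow-up use either measure. A patient interrupted on U = 3.5 who next has a 24-hour collection of P = 2.5 g meets R on that collection, whether or not UPC has fallen.

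**One measure only.** If a site uses only UPC throughout, I reduces to U ≥ 3 and R to U < 3, which cannot both be true; C and I are also exclusive. The same holds for I and R if only the 24-hour value is used. The conflict needs both measures.

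**Comparison within Section 6.0.** Thrombocytopenia interrupts at grade 3 or 4 and restarts at grade 2 or below, which do not overlap. Resumption after grade 3 venous thrombosis, and re-treatment after an ALT rise above 8 times ULN, each require every listed criterion to be met. The proteinuria restart is built differently, on either of two measures.

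**The case against.** The strongest reply is that UPC and the 24-hour collection are alternative assays, that a site follows one of them to resolution, and that each *or* means whichever assay is in use. The calendar supports this in part, since only UPC is scheduled. On that reading no conflict arises. It is a reasonable intention, but the text does not state it, and entering on one measure and leaving on the other stays open.

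A second reply is that Steps 1 and 2 are sequential, so UPC 3.5 with 2.5 g still gives an order of actions: interrupt, monitor, restart lower. That much stands. It does not prevent a restart while UPC remains at or above 3. Nor does it help with UPC 2.5 and 3.5 g, where the first row says not to interrupt at all.

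Three stronger readings are tempting, and the documents do not support them.

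- *A single laboratory value is both event and resolution.* It cannot be, as the one-measure check shows.
- *Inclusion criterion 6i makes the 24-hour value decide at entry, so it should decide here.* The criterion reads "UPC < 1 (in like units) or, if UPC ≥ 1 , 24-hour urine protein < 1 g". A patient with UPC 0.8 and 24-hour protein 1.2 g qualifies on UPC alone, so 6i is met whenever either measure is below 1. It shows that the authors foresaw a raised UPC with a lower 24-hour value. It does not rank the measures, and its either-measure structure resembles the restart condition.
- *Hypertension row (A) has the same fault*, because its trigger "or a clinically significant increase in DBP of 20 mmHg (but still below 110 mmHg" can be met at pressures that footnote a calls well-controlled ("Well-controlled BP defined as SBP <140 mmHg and mean DBP <90 mmHg"). A relative-rise trigger, qualified by clinical significance, can coexist with an absolute target. Row (A) keeps pazopanib at its current dose, and a target already met does not lead to row (B) by that route. This is not a contradiction.

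**Conclusion.** The proteinuria rows contradict themselves as written. In one of the four combinations (UPC below 3, 24-hour protein 3 g or more) two rows give opposite instructions. In both discordant combinations the restart condition is met while the interruption condition still holds.

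The conclusion rests on the literal wording and on both measures being obtained and disagreeing about 3. The 24-hour collection is unscheduled and the documents give no discordance rate, so no count of affected patients out of 56 can be supported. The effect is inconsistent dosing and safety handling between sites. The sample size, the decision rule of 17 or more of 56, and the error rates are unaffected.

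A reader might also infer that a patient with a persistently high UPC would be stepped from 800 to 600, 400 and 200 mg and then stopped within the primary window. The text does not establish this. Steps 3 and 4 require recurrence, and a value that never fell has not plainly recurred. Step 2 monitors weekly, not only at Day 1 visits, and the general rule in Section 6.0 permits re-escalation once toxicity abates. Even if one step were taken at each Day 1 visit from cycle 2, the stop would fall on cycle 5 Day 1, which is day 4 × 28 + 1 = 113, after the nominal 16-week point at day 16 × 7 = 112.

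**What to change.** Reconcile the two proteinuria rows of Section 6.0 so that:

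1. every pair of UPC and 24-hour values leads to exactly one action, including the case where UPC is below 3 and the 24-hour value is not;
2. the restart condition cannot be true while the interruption condition is true;
3. the text says what applies when the two measures disagree, and whether follow-up must use the measure that triggered the interruption.

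The clinical team decides which measure or wording governs; this review does not propose one. Running the four combinations in the table above through the redrafted rows will confirm that the conflict is gone.

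The cost is a wording change to one part of one table, made by protocol amendment. Reconciling the text does not in itself add tests or patients, and the statistical section needs no change.

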5.0 TREATMENT PLAN

5.1 Agent Administration

Pazopanib will be started at a dose of 200 mg BID for four days, then escalated to a dose of 400 mg BID for four days (if tolerated), then escalated once more to a dose of 800 mg QD for the duration of participation (if tolerated) or until dose reduction, if necessary. Pazopanib should be taken orally without food at least one hour before or two hours after a meal. One cycle of pazopanib is 28 days. The tablets should be swallowed whole and must not be crushed or broken. The time of day the tablets are taken should be relatively constant.

If a dose is missed, the subject should take the dose as soon as possible, but only if there are 12 or more hours remaining before the next dose is due. If the next dose is due in less than 12 hours, the subject should skip the missed dose and take the next dose as scheduled.

If vomiting occurs after taking pazopanib, the subject should not take a replacement dose for that dose, but should resume taking pazopanib at the next scheduled dose. If vomiting persists, the subject should be instructed to notify the investigator.

Please note that a Monday or Thursday start is recommended to avoid weekend blood draws for pharmacokinetic testing.

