(C). ALT $>8.0 \times \text{ULN}$ without bilirubin elevation (defined as total bilirubin ^b $<2.0 \times \text{ULN}$ or direct bilirubin $\leq 35\%$) and without hypersensitivity symptoms (e.g., fever, rash)	
1st occurrence – Liver Event Interruption Criteria:
 
Step 1. Interrupt pazopanib until toxicity resolves to \leq grade 1 or baseline. Report the event to Novartis as an SAE within 24 hours of learning of its occurrence. Make every reasonable attempt to have subjects return to the clinic within 24 to 72 hours for repeat liver chemistries and liver event follow up assessments.
 
Step 2. Liver imaging and other laboratory investigations should be considered as clinically appropriate.
 
Step 3. Monitor subject closely for clinical signs and symptoms; perform full panel LFTs^a weekly or more frequently if clinically indicated until ALT is reduced to grade 1.
 
Step 4. If the subject is benefiting from the study treatment, re-treatment with pazopanib at 400 mg may be considered if ALL following criteria are met:
 
 - ALT reduced to Grade 1 - Total bilirubin $<1.5 \times \text{ULN}$ or direct bilirubin $\leq 35\%$ - No hypersensitivity signs or symptoms - Subject is benefiting from therapy. 
Recurrence – Liver Event Stopping Criteria:
 
Discontinue pazopanib permanently and monitor subject closely for clinical signs and symptoms; perform full panel LFTs^a weekly or more frequently if clinically indicated until ALT is reduced to grade 1.

Event	Dose Modification Algorithms

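### After a first ALT above 8 x ULN, Section 6.0 allows re-treatment at a fixed 400 mg whatever the dose at onset, which is no reduction from 400 mg/day and an increase from 200 mg/day.

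*Combined protocol and SAP*

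**What the plan says.** Row (C) of the hepatotoxicity table in Section 6.0 requires interruption at the first occurrence, reporting to Novartis as an SAE within 24 hours, and close liver monitoring. Step 4 then says that, for a subject who is benefiting, "re-treatment with pazopanib at 400 mg may be considered if ALL following criteria are met". The four criteria are ALT back to grade 1, a bilirubin limit, no hypersensitivity, and benefit from therapy. On recurrence the instruction is "Discontinue pazopanib permanently and monitor subject closely for clinical signs and symptoms".

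Section 5.1 sets the starting level: "Pazopanib will be started at a dose of 200 mg BID for four days". A patient moves up to 400 mg twice daily only if the first level is tolerated, and reaches the 800 mg once-daily target only if the second is tolerated too. The opening of Section 6.0 says that, where a reduction is needed, "the dose should be reduced stepwise by 200 mg at each step". Once toxicity has abated with a lower dose, "the pazopanib dose can then be increased step-wise back to the pre-event dose".

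Elsewhere in Section 6.0, the row for other clinically significant drug-related events of grade 2 or 3 says "Restart pazopanib dose-reduced by 200 mg and monitor as clinically indicated". In the hepatotoxicity table itself, row (B), for ALT above 3 and up to 8 x ULN, says "Continue pazopanib at current dose levels".

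**The concern.** Row (C) names one restart dose and does not tie it to the dose the patient was taking when ALT rose. That works for a patient on the 800 mg target. A patient already at 400 mg/day would restart on the same dose at which ALT exceeded 8 x ULN, and a patient at 200 mg/day would restart on twice that dose.

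What is at stake is the dose given after a liver event serious enough to require interruption and SAE reporting. A site that follows the row literally is offered no dose below 400 mg.

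**Working it through.** The plan states no figure to reproduce here. The check compares the fixed restart dose with each possible dose at onset, and then with the other restart rules in Section 6.0.

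**Assumption.** Row (C) gives no dosing frequency. I read 400 mg as the daily total, because Section 5.1 settles on once-daily dosing and the diaries for Cycle 2 onward (Appendix D) allow only a morning dose.

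**Which doses are reachable?**
- 600 mg/day: one step down, 800 - 200 = 600.
- 400 mg/day: the starting dose when escalation is not tolerated, 2 x 200 = 400 (Section 5.1); two steps down, 800 - 2 x 200 = 400 (Section 6.0, opening); or one grade 2 palmar-plantar erythrodysesthesia event, which restarts at 400 mg.
- 200 mg/day: a third step down, 800 - 3 x 200 = 200, or recurrence of that skin event. The Appendix D diary has entries for both two and one 200 mg tablets.

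**Change on re-treatment** = 400 - dose at onset.

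| Daily dose at onset | Restart under row (C) | Change | Relative change |
|---|---|---|---|
| 800 mg | 400 mg | -400 mg | -50% |
| 600 mg | 400 mg | -200 mg | -33% |
| 400 mg | 400 mg | 0 mg | 0% |
| 200 mg | 400 mg | +200 mg | +100% |

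The first two lines are sound. The gap is in the last two.

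**Sensitivity to the assumption.** If 400 mg were taken as a twice-daily dose (800 mg/day), the changes would be 0, +200, +400 and +600 mg, so no patient would have a reduction. The daily-total reading is the one more favourable to the plan.

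**Other interrupt-and-restart rows in Section 6.0**
- Hypertension (B) and (C), proteinuria, grade 3 or 4 thrombocytopenia, and other clinically significant grade 2 or 3 events: restart 200 mg below the previous dose.
- Grade 3 venous thrombosis: resume at a reduced dose.
- Grade 2 palmar-plantar erythrodysesthesia: a fixed 400 mg, but described as a reduction, with 200 mg or stopping to be considered on recurrence.
- Grade 2 bleeding: a reduction is only to be considered. This is the exception.

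Proteinuria also deals with the lowest dose: if the event recurs and no further reduction is possible, treatment stops. Row (C) neither calls for a reduction nor says what happens at the lowest dose. For a patient at 400 mg/day, the row for other events gives 400 - 200 = 200 mg, while row (C) gives 400 mg.

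**The case against.** The strongest reply is that no rule is broken. Row (C) never says that the restart must be a reduction, and the 200 mg step in the opening of Section 6.0 applies only where a reduction is necessary. The hepatotoxicity table also has its own logic: row (B) keeps the dose unchanged up to 8 x ULN, and row (D) stops the drug. On this view, the other rows show a difference rather than an inconsistency. This stands as far as it goes: a reduction is not mandatory anywhere for this event. But row (B) involves no interruption. Row (C) is where the table chooses to interrupt and name a restart dose, and the dose it names does not work at the lower levels.

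The second reply is that safeguards cover the consequence. Re-treatment is optional, four criteria must be met, liver tests continue at least weekly until ALT is grade 1, and recurrence means permanent discontinuation. Section 5.4 also ends treatment when the investigator judges that an event may cause severe or permanent harm. These limit the harm, but none sets the restart dose, and the recurrence rule acts only after a second liver event.

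The third reply is that few patients are involved. The benefit criterion narrows the group further: the first response evaluation is at 8 weeks (Section 12.1), so a patient held at the starting dose by early intolerance has no scheduled scan showing benefit before then. This also stands.

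A reader might infer that the 200 mg/day case directly contradicts the re-escalation paragraph in Section 6.0, which goes no higher than the pre-event dose. The documents do not support that. The paragraph is written for toxicity that abated with a lower dose, whereas row (C) deals with interruption and recovery.

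**Conclusion.** The point holds as a minor safety wording error. Read literally, with 400 mg as the daily total, row (C) Step 4 gives no reduction from 400 mg/day and a doubling from 200 mg/day after an SAE-level ALT event. Most other restart rows in the same section require a reduced dose. Restarts from 800 and 600 mg/day are not affected.

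A reader might infer that re-treatment at 400 mg is unsafe for these patients. The documents do not show that: they give no relationship between dose and ALT, and row (B) continues the current dose at lower elevations. The conclusion is only that the restart is not a reduction. Nor is any effect on the primary endpoint, sample size or power claimed. The documents give no frequency for the event or for these dose levels, so the number affected is unknown. It should be small, because it requires a low dose at onset, a first ALT above 8 x ULN, recovery, judged benefit and a decision to re-treat.

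**What to change.** In row (C), first occurrence, Step 4, replace the fixed 400 mg with: *at a reduced dose of no more than 400 mg/day (200 mg/day if onset was at 400 mg/day); if onset was at 200 mg/day, do not re-treat*.

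Under this wording 800 and 600 mg/day can still restart at 400 mg/day, 400 mg/day goes to 200 mg/day, and 200 mg/day stops. Stopping at the lowest dose follows the same principle as the proteinuria row. Writing mg/day also removes the doubt about dosing frequency.

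The cost is one phrase at the next amendment, with no extra visits, data or patients. The downside is that a few patients who are benefiting would restart at a lower dose or stop. The final dose levels are for the sponsor's clinicians to confirm.
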